**Table 7: Dose Escalation Criteria**

Number of Subjects per Cohort with DLT During Treatment Period	Dose Escalation Decision
0 out of 3	Enter 3 subjects at the next dose level.
1 out of 3	Enter 3 more subjects at this dose level.  If no additional DLT, proceed to the next dose level.  If an additional DLT occurs (i.e. $\geq$ 2 DLTs/6 subjects), dose

	escalation is stopped and the previous dose level is declared the MTD.
≥ 2	The previous dose level is declared MTD. There is no advancement to higher dose levels.

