#### **5.3 Dose Escalation and Stopping Rules**

The dose-limiting toxicity (DLT), as defined in Section 5.5, will be the basis for determining the maximum tolerated dose (MTD). Any subject who receives at least one dose of the study drug (BKM120) will be included in analysis for DLT. Treatment cohorts will be dosed in escalating order, as outlined in Table 8, only after the safety of the previous dose level has been established, or until an MTD has been determined.

Subsequent dose levels will be opened for treatment as follows:

1) Escalation to the subsequent dose level will occur only after all subjects in the previous cohort have completed the full 7-week course of BKM120-CRT and have been evaluated for safety and toxicity. Safety will be evaluated based on the incidence of adverse events (AEs), physical exam findings, and clinical laboratory test results. A review of the safety data for each cohort will be conducted when all of the above data are available. In the event that an MTD is not reached after dose level 5, the study will be considered to have reached a biologically acceptable dose appropriate for Phase II study. Any further dose escalations or de-escalations will require a protocol amendment.

2) Three patients will initially be enrolled at dose level 1. The following rules apply for the advancement to the next dose level and to determine the MTD (see also Table 7). Enrollment may proceed at the higher dose according to the rules after three patients have been treated for the 2 weeks of BKM120 followed by 7 weeks of BKM120+CRT at a given dose level and safety data have been reviewed. The dose will be increased until a DLT is observed in one subject. Dose limiting toxicity is graded according to the National Cancer Institute’s CTCAE v4.0 (<http://ctep.cancer.gov/forms/CTCAEv4.pdf>).

Once a DLT occurs, additional subjects will be added to the cohort until either a second subject experiences a DLT or six subjects are treated at that dose level. If no additional subject experiences a DLT at the trigger dose-level, further dose escalation as outlined in Table 8 will be explored in cohorts of three subjects.

If two or more subjects experience a DLT at a given dose, then three additional subjects will be treated at the next lower dose, unless six subjects have already been treated at that dose.

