The maximum tolerated dose is the highest dose studied for which the incidence of DLT is less than 33%. The final cohort of three to six subjects may be expanded to 10 subjects to provide additional safety and pharmacokinetic data.

The decision to enroll subjects in the next higher dose level will be made at the discretion of the principal investigator.

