**Table 8: Dose Escalation**

Dose level	BKM120 (mg, daily)	Cisplatin (mg/m  , weekly)
-1	20	30
1	40	30
2	40	35
3	40	40
4	60	40
5	80	40
6	100	40

BKM120 will start **2 weeks** prior to first dose of cisplatin and radiation start.

Patients will be assessed weekly for adverse events for the duration of the treatment (2 weeks of BKM120 and 7 weeks of BKM120+CRT = 9 weeks) and every 2 weeks after conclusion of CRT during the first month, then monthly for 3 months, then every 3 months until first progression, death, or 2 years post study entry whichever occurs first.

After establishment of MTD, 10 additional patients will be enrolled at the MTD dose level to gain additional experience with this regimen and dose. If the MTD is not reached, because ≤ 1 DLT is encountered at dose level 6, ten additional patients will be enrolled at this dose level. If there are greater than 2 DLTs at dose level 1, enrollment will continue at dose level -1 with no advancement beyond dose level -1.

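### Section 5.3 gives two unranked rules for naming the MTD after two or more DLTs; the effect on dose is modest, but the primary decision rule should be made single

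*Combined protocol and SAP*

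**What the plan says.** Section 13 states that the trial is a standard 3+3 whose primary endpoint is the MTD, and it refers to section 5.3 for the rules.

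**After two or more DLTs.** Both stopping rows of Table 7 name the previous level. The row for one DLT in three followed by another reads "escalation is stopped and the previous dose level is declared the MTD". The last row reads "The previous dose level is declared MTD. There is no advancement to higher dose levels". The text of section 5.3, item 2, differs: "If two or more subjects experience a DLT at a given dose, then three additional subjects will be treated at the next lower dose", with the exception "unless six subjects have already been treated at that dose".

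**Definition.** Section 5.3 then says "The maximum tolerated dose is the highest dose studied for which the incidence of DLT is less than 33" (per cent), and it refers to a final cohort of three to six.

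**Level -1.** The text after Table 8 says "If there are greater than 2 DLTs at dose level 1, enrollment will continue at dose level -1".

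**Last level.** Item 1 of section 5.3 says what happens "In the event that an MTD is not reached after dose level 5" and adds "Any further dose escalations or de-escalations will require a protocol amendment". Table 8 lists level 6 (100 mg BKM120), the text after it plans the ten-patient expansion at level 6 if that level is tolerated, and section 13 counts six levels.

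**The concern.** A dose-finding algorithm should give one answer from one set of DLT data. Suppose level 4 fails and level 3 was cleared with no DLT in three patients. Table 7 makes level 3 the MTD on three patients. The text requires three more there first. If two or more of those three have a DLT, the level stands at 2/6 or worse, which is at least 33.3% and fails the definition, so the text would reject the dose that Table 7 declares.

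The definition does not settle the matter. A level at 0/3 already meets it, and a final cohort of three is allowed. Item 2 cites Table 7 as a cross-reference and does not say which prevails. What is at stake is which dose is declared the MTD and given to the ten expansion patients.

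Two slips add to the uncertainty at the ends of the dose range. At the bottom, the sentence after Table 8 does not cover exactly two DLTs at level 1, and Table 7 read literally would name level -1 with nobody treated there, although the definition asks for a dose that was studied. At the top, item 1 stops one level short of Table 8.

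**Working it through.** **The plan's own figures.** With p the true DLT rate and q = 1 - p, a level is passed on 0/3, or on 1/3 followed by 0/3: P(escalate) = q³ + 3pq² × q³.

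- p = 20%: 0.512 + 0.384 × 0.512 = 0.709
- p = 30%: 0.343 + 0.441 × 0.343 = 0.494
- p = 40%: 0.216 + 0.432 × 0.216 = 0.309
- p = 50% and 60%: 0.172 and 0.082

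Section 13 prints .71, .49, .31, .17 and .08, so its table reproduces. It covers only the upward step and is the same under either MTD rule. The maximum of 46 also reproduces as 6 × 6 + 10. A last level of 5 would give 5 × 6 + 10 = 40.

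**Assumed DLT rates.** The documents give none by level. I take three rising curves over levels 1-6, with level 6 as the last:

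- low: 5, 10, 15, 20, 30, 40%
- middle: 10, 15, 20, 30, 40, 50%
- high: 20, 25, 30, 40, 50, 60%

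**When the two rules part.**

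1. P(stop at level k) = product of P(escalate) over the levels below k, times 1 - P(escalate) at k.
2. The instructions diverge if k is above 1 and level k-1 was cleared on 0/3, which has probability q³ / P(escalate) at level k-1.
3. The declared MTD then differs if two or more of the three added patients have a DLT. That probability is 0.104, 0.216 and 0.352 at true rates of 20%, 30% and 40%.

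Middle curve, step by step:

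| Stop at level | P(stop) | Previous level cleared on 0/3 | Diverge | P(2+ of 3) | MTD differs |
|---|---|---|---|---|---|
| 2 | 0.169 | 0.805 | 0.136 | 0.028 | 0.004 |
| 3 | 0.215 | 0.755 | 0.162 | 0.061 | 0.010 |
| 4 | 0.264 | 0.723 | 0.191 | 0.104 | 0.020 |
| 5 | 0.178 | 0.694 | 0.124 | 0.216 | 0.027 |
| 6 | 0.066 | 0.698 | 0.046 | 0.352 | 0.016 |
| Sum | 0.892 | | 0.659 | | 0.077 |

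**Is the Table 7 dose too toxic?** On the middle curve, levels 5 and 6 exceed one third. Table 7 declares one of them with probability 0.066 + 0.014 = 0.080. Filling to six removes 0.016 from level 5, leaving 0.064. The same enumeration on all three curves gives:

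| | Low | Middle | High |
|---|---|---|---|
| Instructions diverge, all trials | 68% | 66% | 50% |
| Declared MTD differs, all trials | 6% | 8% | 8% |
| Declared level truly above one third, Table 7 | 7.8% | 8.0% | 6.5% |
| Declared level truly above one third, text rule | 7.8% | 6.4% | 5.1% |
| Table 7 dose truly below one third, when the MTDs differ | 100% | 79% | 80% |

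**Exactly two DLTs at level 1.** With full added cohorts of three, P(exactly 2) = P(2/3) + P(1/3) × P(1/3), and P(fail) = 1 - P(escalate).

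- 20%: 0.096 + 0.384² = 0.243; 0.243 / 0.291 = 84% of failures
- 30%: 0.189 + 0.441² = 0.383; 0.383 / 0.506 = 76%
- 40%: 0.288 + 0.432² = 0.475; 0.475 / 0.691 = 69%

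Level 1 itself fails in 3%, 9% and 29% of trials on the low, middle and high curves.

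**Level 5 or level 6.** This matters only if levels 1-5 are all cleared: 25%, 8% and 1% of trials on the three curves.

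**The case against.** The strongest reply is that a careful team could read the passages together. Item 2 points to Table 7, which can be taken as a summary of the text: treat three more at the lower level, then apply the definition, which rejects 2/6. That is a workable reading, but it is inferred. Taken literally, Table 7 declares the MTD with no added patients, and no passage says it gives way.

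A reader might infer that Table 7 sends the expansion cohort to an unsafe dose. The numbers do not support that. When the two rules name different doses, the Table 7 dose is truly below one third in 79-100% of cases on these curves, so the text rule is usually rejecting an acceptable dose by chance.

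A reader might also infer that the sentence after Table 8 contradicts the step-down rule. It does not. It is silent at exactly two DLTs, the text covers that case by stepping down at two or more, and nothing permits carrying on at level 1. Likewise the level 5 wording is probably a slip, because Table 8, the text after it, the maximum of 46 and the 100 mg step in the section 6 reduction schedule all point to level 6. If followed, it errs toward the lower dose.

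Safeguards exist. Section 5.2 requires an amendment to declare the dose, the monitoring committee may receive DLT data (section 12.2), and ten more patients are treated at the MTD. They limit harm, but none says which rule applies. The plan also accepts expansion at level 6 with at most one DLT, which could be 0/3. That shows tolerance for three patients at the top level, but does not decide what happens after a stop.

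**Conclusion.** The point holds and should be fixed. Section 5.3 is wrong as written, because two unranked rules for the primary endpoint can give different MTDs from the same data. Under the assumed curves the instructions diverge in about 50-68% of trials, the declared MTD differs in about 6-8%, and the chance of declaring a level truly above one third moves by 0 to 1.6 points. These figures rest on curves I chose and on added cohorts of exactly three.

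The case for the change is the ambiguity of the rule; a large shift in dose or a safety failure is not shown. Section 13's escalation probabilities are correct. The level -1 trigger and the last level are related slips that other passages resolve.

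**What to change.** - **Table 7, both stopping rows:** escalation stops; the previous level is filled to six patients if fewer have been treated, and is the MTD only if at most 1 of 6 has a DLT; otherwise the next lower level in Table 8, down to level -1, is assessed the same way.
- **Text after Table 8:** make the trigger for level -1 two or more DLTs at level 1.
- **Section 5.3, item 1:** change level 5 to level 6, and limit the amendment sentence to escalations or de-escalations beyond the levels in Table 8. Otherwise it would clash with the step-down.

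The cost is wording, plus up to three more patients at a level cleared on 0/3, within the six per level already planned. Section 13's escalation probabilities do not change. A full step-down through level -1 could in principle reach 7 × 6 + 10 = 52 patients. Exceeding 46 has a probability of about one in a million or less on these curves, with level -1 assumed at 5%, so the stated maximum can stand.

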**Table 8: Dose Escalation**

Dose level	BKM120 (mg, daily)	Cisplatin (mg/m  , weekly)
-1	20	30
1	40	30
2	40	35
3	40	40
4	60	40
5	80	40
6	100	40

BKM120 will start **2 weeks** prior to first dose of cisplatin and radiation start.

Patients will be assessed weekly for adverse events for the duration of the treatment (2 weeks of BKM120 and 7 weeks of BKM120+CRT = 9 weeks) and every 2 weeks after conclusion of CRT during the first month, then monthly for 3 months, then every 3 months until first progression, death, or 2 years post study entry whichever occurs first.

After establishment of MTD, 10 additional patients will be enrolled at the MTD dose level to gain additional experience with this regimen and dose. If the MTD is not reached, because ≤ 1 DLT is encountered at dose level 6, ten additional patients will be enrolled at this dose level. If there are greater than 2 DLTs at dose level 1, enrollment will continue at dose level -1 with no advancement beyond dose level -1.

#### **5.4 Interruption or discontinuation of treatment**

For patients who are unable to tolerate the protocol-specified dosing schedule, dose adjustments are permitted in order to keep the patient on study drug. If administration of BKM120 must be interrupted because of unacceptable toxicity, drug dosing will be interrupted or modified according to rules described in Table 9. Toxicity will be assessed using the NIH-NCI Common Terminology Criteria for Adverse Events, version 4.0.

[http://evs.nci.nih.gov/ftp1/CTCAE/CTCAE\\_4.03\\_2010-06-14\\_QuickReference\\_8.5x11.pdf](http://evs.nci.nih.gov/ftp1/CTCAE/CTCAE_4.03_2010-06-14_QuickReference_8.5x11.pdf)

#### **5.5 Dose-Limiting Toxicity**

Toxicity will be assessed using the NCI Common Toxicity Criteria for Adverse Events, version 4.0

[http://evs.nci.nih.gov/ftp1/CTCAE/CTCAE\\_4.03\\_2010-06-14\\_QuickReference\\_8.5x11.pdf](http://evs.nci.nih.gov/ftp1/CTCAE/CTCAE_4.03_2010-06-14_QuickReference_8.5x11.pdf) unless

otherwise specified (e.g., hyperglycemia). A dose-limiting toxicity (DLT) is defined as an adverse event or abnormal laboratory value assessed as unrelated to disease, disease progression, inter-current illness, or concomitant medications, and occurs < 28 days following the last dose of BKM120, and meets any of the criteria listed in Table 9.

Whenever a patient experiences toxicity that fulfills the criteria for a DLT (or a potential DLT), treatment with BKM120 will be interrupted (if not otherwise specified) and the toxicity will be followed up as described in section 5.3. Exceptions are CTCAE grade 2 hyperglycemia and CTCAE grade 2 mood alteration, where BKM120 treatment will be continued under appropriate co-medication. The criteria for dose-limiting toxicities are outlined in Table 9.

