### **5. TREATMENT PLAN**

#### **5.1 Treatment Regimen**

The investigational therapy used in the course of this study is BKM120. Treatment with BKM120 starts 2 weeks prior to cisplatin and radiotherapy and continues until the end of radiotherapy.

Study medication will be self-administered by the patients continuously throughout radiation. In order to assure compliance with protocol procedures drug administration will be thoroughly explained to the patients. During the study, BKM120 will be administered orally. It is given every day including weekend days. Administration of BKM120 stops with the end of radiotherapy. If radiation is held due to toxicity, BKM120 and cisplatin will be held as well. If cisplatin is held due to toxicity, BKM120 and radiation will continue. If BKM120 is held due to toxicity, cisplatin and radiation will continue. Medication labels will comply with US legal requirements and be printed in English. The storage conditions for study drug will be described on the medication label.

BKM120 will be provided by Novartis Pharmaceuticals free of charge. BKM120 is formulated as capsules for oral administration of 10mg and 50mg strength. Capsules are packaged in bottles. BKM120 capsule cannot be crushed and has to be swallowed. It cannot be given via enteral feeding tube.

If vomiting occurs, no attempt should be made to replace the vomited dose.

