## 5.6 Follow-up for dose-limiting toxicities

Patients whose treatment is interrupted or permanently discontinued due to an adverse event or clinically significant laboratory value, must be followed as outlined in Table 10, at least once a week for 4 weeks, and subsequently at 4-week intervals, until resolution or stabilization of the event, whichever comes first. If a patient requires a dose delay of > 14 days from the intended day of the next scheduled dose, then the patient should be discontinued from the treatment but will only come off study if dead or due to refusal to continue on the study. All patients must be followed for adverse events and serious adverse events for 28 days following the last dose of BKM120.

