## APPENDIX B: DRUGS THAT ARE PROHIBITED

- Other investigational therapies must not be used while the patient is on the study.
- Anticancer therapy (chemotherapy, biologic or radiation therapy, and surgery) other than the study treatments must not be given to patients while the patient is on the study. If such agents are required for a patient then the patient must be discontinued from the study.
- In *vitro* metabolism studies suggest that oxidative metabolism of BKM120 is predominantly mediated by CYP3A4 (fm>0.9), with only minor contributions of CYP1A1. As BKM120 is a sensitive CYP3A4 substrate, co-administration of BKM120 with strong and moderate CYP3A4 inhibitors and CYP3A4 inducers is prohibited. See below for a list of prohibited drugs. Please note this list may not be comprehensive.
- Based on in vitro studies, co-administration of BKM120 with CYP3A4 inducers is predicted to decrease the systemic exposure to BKM120, thereby increasing the risk of exposing the patient to subtherapeutic drug levels. See below for a list of prohibited CYP3A inducers. Please note that this list may not be comprehensive. Therapeutic doses of warfarin sodium (Coumadin®) or any other coumadin-derivative anticoagulants are not permitted.
- If a patient requires the concomitant use of any medication included in Table 18 below entitled “List of Prohibited QT prolonging drugs” (i.e., drugs that are generally accepted by the Qtdrugs.org Advisory Board of the Arizona CERT to have a risk of causing Torsades des de Pointes), study treatment administration must be interrupted as long as the patient requires therapy with the QT prolonging agent.
- Herbal preparations/medications are not allowed throughout the study. These herbal medications include, but are not limited to St. John’s wort, Kava, ephedra (ma huang), ginko biloba, dehydroepiandrosterone (DHEA), yohimbe, saw palmetto, ginseng. Patients should stop using these herbal medications 7 days prior to first dose of study drug.
- Hormonal contraceptives may be affected by cytochrome P450 interactions, and are therefore not considered effective in this study.

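### If BKM120 stops early without a DLT, the DLT window in section 5.5 can close before chemoradiation ends while the patient stays in the DLT denominator

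*Combined protocol and SAP*

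**What the plan says.** The primary objective (section 1.2) is the MTD of BKM120 and cisplatin given with radiation. In Table 8, levels 1 to 3 hold BKM120 at 40 mg and raise only cisplatin (30, 35, 40 mg/m²).

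Section 5.5 limits a DLT to an event that "occurs < 28 days following the last dose of BKM120". Section 5.3 sets the denominator: "Any subject who receives at least one dose of the study drug (BKM120) will be included in analysis for DLT". It gives no minimum exposure and no replacement rule. Table 7 counts DLTs during a treatment period that is not defined.

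Section 5.1 governs how the components stop. On plan, "Administration of BKM120 stops with the end of radiotherapy". Otherwise, "If radiation is held due to toxicity, BKM120 and cisplatin will be held as well", but "If BKM120 is held due to toxicity, cisplatin and radiation will continue". Sections 5.6 and 5.8.1 take a patient off treatment after a delay of more than 14 days but keep the patient on study. Section 5.6 also ties safety follow-up to BKM120: "All patients must be followed for adverse events and serious adverse events for 28 days following the last dose of BKM120".

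**The concern.** The trial tests a three-part regimen, but the clock for its primary endpoint follows only one part. A patient who stops BKM120 early without a DLT, and goes on with cisplatin and radiation, can have a Table 9 event during chemoradiation that falls outside the window. That patient stays in the denominator and scores zero.

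The error has one direction: the observed DLT rate can only be too low, which favours escalation and a higher MTD. At levels 2 and 3 the cisplatin doses given after the window closes are the very ones being escalated. Cohorts have 3 to 6 patients, so one unscored event can turn 1 of 3 into 0 of 3 (escalate instead of expand) or 2 of 6 into 1 of 6 (escalate instead of stop).

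**Working it through.** **1. The plan's own figures.** For the 3+3 rule in Table 7, P(escalate) = (1−p)³ + 3p(1−p)² × (1−p)³. For p = 20, 30, 40, 50 and 60% this gives 0.709, 0.494, 0.309, 0.172 and 0.082. The section 13 table (.71, .49, .31, .17, .08) is reproduced. It assumes that every DLT is counted.

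**2. Calendar.** Study day 1 is the first BKM120 dose. After the two-week lead-in, day 1 of chemoradiation (CRT) is study day 15. Cisplatin falls on CRT days 1, 8, 15, 22, 29, 36 and 43 (section 5.8.2), the last being study day 57. Radiation is 35 fractions, five per week (section 5.9). With a Monday start and no breaks (an assumption), the last fraction is on CRT day 47, study day 61. The nominal end of treatment is study day 63 (Table 8 text: "2 weeks of BKM120 and 7 weeks of BKM120+CRT = 9 weeks").

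**3. Where the window closes.** With the last BKM120 dose on study day d, the last countable day is d + 27.

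| Last BKM120 dose | d | Window's last CRT day | Cisplatin doses after | Fractions after |
|---|---|---|---|---|
| Lead-in day 8 | 8 | 21 | 4 of 7 | 20 of 35 |
| Lead-in day 14 | 14 | 27 | 3 of 7 | 15 of 35 (30 of 70 Gy) |
| CRT day 7 | 21 | 34 | 2 of 7 | 10 of 35 |
| CRT day 14 | 28 | 41 | 1 of 7 | 5 of 35 |
| CRT day 19 | 33 | 46 | 0 | 1 of 35 |
| End of radiotherapy | 61–63 | 74–76 | 0 | 0 |

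The window closes before the last fraction only if d + 27 < 61, so d ≤ 33. It closes before nominal day 63 only if d ≤ 35, and before the last cisplatin dose (day 57) only if d ≤ 29.

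**4. Who is left in the gap.** Table 9 already makes most grade 3 or higher events DLTs. Its notes add that a lower-grade event causing more than 7 missed BKM120 doses is a DLT. A permanent stop by day 35 misses about 28 or more of the 63 planned doses, so on the natural reading a toxicity-driven stop counts. Three routes remain:

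- A prohibited QT-prolonging drug is needed. Appendix B then says "study treatment administration must be interrupted as long as the patient requires therapy with the QT prolonging agent", and a long need leads to the 14-day rule.
- The patient declines the capsules but stays on study.
- The event is attributed to disease, inter-current illness or other medication, which section 5.5 excludes from DLTs. Loss of swallowing from the tumour is a plausible case, because section 5.1 rules out giving the capsules by feeding tube.

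**5. One event, two scores.** Take a last BKM120 dose on lead-in day 14 and a Table 9 event on CRT day 40 (study day 54). Under section 5.5 the window closed on CRT day 27, so there is no DLT. If Table 7's treatment period means the nine weeks to study day 63, the event is a DLT.

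**6. Illustrative size.** Neither input below is in the documents. Let f be the share of patients who stop early without a DLT and s the share of their DLT risk after closure. The observed rate is p(1 − f·s). Over f = 10–30% and s = 25–75%:

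| True rate | Stated P(escalate) | With the gap |
|---|---|---|
| 20% | .71 | 0.72–0.80 |
| 30% | .49 | 0.51–0.64 |
| 40% | .31 | 0.33–0.47 |
| 50% | .17 | 0.19–0.33 |
| 60% | .08 | 0.09–0.21 |

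Example: p = 40%, f = 20%, s = 50% gives an observed rate of 0.40 × 0.90 = 36% and P(escalate) = 0.38. Within one cohort of three at p = 30% and s = 50%, P(0 DLTs) is 0.7³ = 0.34 with no such patient, 0.7² × 0.85 = 0.42 with one, and 0.7 × 0.85² = 0.51 with two.

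**The case against.** A reader might infer that DLTs late in chemoradiation go uncounted in general. The documents do not support that: for anyone treated as planned, the window covers all of chemoradiation and almost 28 days more. A reader might also take the section 5.1 rule on toxicity holds as the main source of the gap. It is not, because the note on more than 7 missed doses turns most such stops into DLTs.

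The remaining routes are partly inferred. Section 5.1 says that cisplatin and radiation go on when BKM120 is held for toxicity; nothing says so for a prohibited drug or refused capsules. Appendix B and sections 5.6 to 5.8.1 do not say which components the word treatment covers. Equally, nothing says that chemoradiation ends, and under section 3.2 it is the patient's primary curative treatment.

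Late events would not be invisible. Section 5.3 asks for a safety review after the full course and leaves escalation to the investigator, grade 2 or higher events are reviewed before escalation, and section 12.2 adds a monitoring committee. This stands as a safeguard, but Table 7 and the MTD rule (DLT incidence below 33%) use DLTs only. Section 5.8.1 also says that discontinued patients need only a 28-day visit after the last BKM120 dose, which leaves it unclear whether the weekly visits apply to them.

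The strongest point is that an early stopper tells little about the combination. With an effective half-life of 38 to 49 hours (section 2.2.8.8), 28 days (672 hours) is about 14 to 18 half-lives, so later toxicity belongs to cisplatin and radiation. Part of this stands: the missing evaluability or replacement rule is a related weakness that a longer window does not cure. But while section 5.3 keeps these patients in the denominator, scoring them as having tolerated the level is the less cautious error.

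**Conclusion.** The point holds for a defined minority: patients whose last BKM120 dose falls by about study day 33 to 35 and who have met no DLT criterion. For them a Table 9 event late in chemoradiation is not a DLT under section 5.5, might be one under Table 7, and the patient counts in the denominator either way. The direction is certain, towards escalation, and includes levels 2 and 3, where only cisplatin rises. Completers are unaffected.

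The amount of treatment left uncovered follows from the protocol's calendar, assuming a Monday start and no breaks. The probability shifts do not: they rest on assumed values of f and s and are illustrative only. With f = 10% and s = 50%, the shift at a true rate of 30% is small, from 0.49 to 0.53. The change is worth making because it is cheap, concerns the primary endpoint, and removes a conflict between section 5.5 and Table 7.

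**What to change.** In section 5.5, end the DLT window less than 28 days after the latest of the last BKM120 dose, the last cisplatin dose and the last radiation fraction. Define the treatment period in Table 7 as that same window. Align the 28-day follow-up wording in sections 5.6, 5.7 and 5.8.1, so that events in patients who stop BKM120 early are collected for as long as they can count.

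The cost is a few sentences. Table 17 already has weekly visits during chemoradiation and visits every two weeks in the first month after it. The window for completers stays essentially as it is, since BKM120 and radiotherapy end together.

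The downside is that some toxicity arising after BKM120 has stopped will count. For example, Table 9 counts any one-grade rise in neurotoxicity, and section 5.8.2 lists neuropathy as a cisplatin effect. That is slightly conservative. Which components continue after a non-toxicity stop of BKM120 is a clinical matter on which sections 5.1, 5.6, 5.7, 5.8.1 and Appendix B must be reconciled; the counting rule works whichever way that is settled.
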